#### 5.5.3.1 Infusion-related reactions

IRRs are defined as any signs or symptoms experienced by participants during the infusion of pharmacologic or biologic agents or any event occurring during or within 1 day of drug administration. IRRs are common ADRs with monoclonal antibodies timely related to drug administration and have been reported as anaphylaxis, anaphylactoid reactions, and cytokine release syndrome, among other terms used. IRRs are important identified risks (adverse reactions) for M7824, and the precautions and management are provided in Table 46

A. Signs and symptoms of infusion related reactions (IRRs) including hypersensitivity include but not limited to pyrexia, chills, flushing, hypotension, dyspnea, wheezing, back pain, abdominal pain, and urticaria, were reclassified as important identified risks (adverse reactions).

B. Management

# Table 6: Treatment Modification for Symptoms of Infusion-related Reactions Caused byM7824

NCI-CTCAE Grade	Treatment Modification for M7824

 
Grade 1 – mild
 
Mild transient reaction; infusion interruption not indicated intervention not indicated.
 
	
 
Decrease the M7824 infusion rate by 50% and monitor closely for any worsening.
 

	• The total infusion time for M7824 should not exceed 120 minutes

 
Grade 2 – moderate
 
Therapy or infusion interruption indicated but responds promptly to symptomatic treatment (for example, antihistamines, NSAIDs, narcotics, IV fluids); prophylactic medications
 
	
 
Stop M7824 infusion.
 
Resume infusion at 50% of previous rate once infusion-related reaction has resolved or decreased to at least Grade 1 in severity, and monitor closely for any worsening
 

 
Grade 3 or Grade 4 – severe or life-threatening
 
Grade 3: Prolonged (for example, not rapidly responsive to symptomatic medication and / or brief interruption of infusion); recurrence of symptoms following initial improvement; hospitalization indicated for clinical sequelae.
 
Grade 4: Life-threatening consequences;
 
	
 
Stop the M7824 infusion immediately and disconnect infusion tubing from the subject.
 
Subjects have to be withdrawn immediately form M7824 treatment and must not receive any further M7824 treatment
 

IV = intravenous; NCI-CTCAE = National Cancer Institute – Common Terminology Criteria for Adverse Event; NSAIDs = nonsteroidal anti-inflammatory drugs

#### Additional Modifications for Subjects with Grade 2 Infusion-related Reactions

If, in the event of a Grade 2 infusion-related reaction that does not improve or worsens after implementation of the modifications indicated in **Table 7** (including reducing the infusion rate by 50%), the Investigator may consider treatment with corticosteroids and the infusion of IMP should be stopped for that day. At the next infusion, the Investigator may consider the addition of H2-blocker antihistamines (for example, famotidine or ranitidine), in addition to premedication, for select subjects. However, prophylactic steroids are NOT permitted. If the subject has a second infusion-related reaction Grade  $\geq 2$  on the slower infusion rate, with or without the addition of further medication to premedication, the infusion should be stopped and the subject removed from M7824 treatment.

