#### Table 10: Toxicity stopping boundaries for Cohort B

The operating characteristics for toxicity monitoring in cohort B are illustrated in Table 11.

True toxicity rate	Prob (stop early)	Average Sample Size
0.10	0.25	28.5
0.20	0.238	24.9
0.30	0.623	18.4
0.40	0.900	12.3
0.50	0.989	8.7

Table 11: Operating Characteristics for Toxicity Monitoring in Cohort B

The stopping boundaries and the operating characteristics for cohorts A-C and B were generated using Shiny application for Bayesian toxicity monitoring (http://qctrlshiny/postprobtoxicity).

AEs of 3 or greater and deemed related to M7824 (section 6.4.1.1.1) will count towards toxicity calculations with respect to interim safety monitoring. AEs of 3 or greater deemed unrelated to M7824 are not included towards safety decision making. These include AEs attributable to disease progression (section 6.4.1.1.2) and abnormal laboratory or investigational values that are asymptomatic or do not result in treatment discontinuation (section 6.4.1.1.1).

The time period that grade 3 AEs attributable to M7824 are counted towards interim safety monitoring decisions is defined from their onset to 90 days after the last dose of study drug (section 6.4.1.1.3).

Any grade 5 event on-study will require suspension of the study pending review of the safety data regarding the death.

The Investigator is responsible for completing an efficacy/safety summary report, and submitting it to the IND Office Medical Affairs and Safety Group, for review and approval. This should be submitted after the first 5 evaluable patients per cohort, complete 1 cycle of study treatment, and every 5 evaluable patients per cohort, thereafter. On every report submission, the information from previous reported patients will need to be updated.

A copy of the cohort summary should be placed in the Investigator's Regulatory Binder under "IND Office correspondence".

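### Section 5.5.3.1 gives opposite dosing instructions for an infusion reaction that fails to respond to interruption and treatment, or returns after resumption: Table 6 ends M7824, and the paragraph below it plans another infusion

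*Combined protocol and SAP*

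**What the plan says.** Table 6 in Section 5.5.3.1 sets grade and action together.

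- **Grade 2:** "Therapy or infusion interruption indicated but responds promptly to symptomatic treatment". The infusion is stopped, and the next step is "Resume infusion at 50% of previous rate once infusion-related reaction has resolved or decreased to at least Grade 1 in severity".
- **Grade 3:** "Prolonged (for example, not rapidly responsive to symptomatic medication and / or brief interruption of infusion); recurrence of symptoms following initial improvement". Grades 3 and 4 share one action: the infusion is disconnected, the subject is withdrawn at once, and the subject "must not receive any further M7824 treatment".

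The paragraph directly below, headed as additional modifications for Grade 2 reactions, applies "in the event of a Grade 2 infusion-related reaction that does not improve or worsens after implementation of the modifications". The modifications expressly include halving the infusion rate. Corticosteroids may be considered, and "the infusion of IMP should be stopped for that day. At the next infusion, the Investigator may consider the addition of H2-blocker antihistamines". Removal from M7824 comes only with a second reaction of Grade 2 or higher at the slower rate. For the modifications the paragraph points to Table 7, which is the laboratory panel.

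Section 7.6 states which events enter the Bayesian safety rule: "AEs of 3 or greater and deemed related to M7824 (section 6.4.1.1.1) will count towards toxicity calculations".

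**The concern.** The paragraph's trigger describes a reaction that has not done what Table 6 requires of a Grade 2 reaction. If it fits Table 6's Grade 3 wording instead, an investigator at the chairside has two adjacent instructions: one ends M7824 for that subject, and the other prepares the next dose. The subject could be re-exposed, or permanently withdrawn, depending on which text is read.

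The grade also matters elsewhere. Section 7.6 counts related events of Grade 3 or higher and ignores Grade 2, so a label taken from a management paragraph could affect a cohort's toxicity count.

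**Working it through.** **Step 1. Compare the trigger with the Table 6 definitions.** No arithmetic applies here.

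- *The reaction does not improve after the infusion is stopped and symptoms are treated.* Table 6's Grade 2 requires a prompt response, which is absent. Table 6's Grade 3 includes "Prolonged (for example, not rapidly responsive to symptomatic medication and / or brief interruption of infusion", which fits. Table 6 ends M7824; the paragraph stops for the day and continues.
- *The reaction settles, the infusion is resumed at half rate, and the reaction returns.* Table 6 allows resumption after a Grade 2 stop only once the reaction has resolved or fallen to Grade 1, so there has been improvement first. Symptoms that return after that fit the second Grade 3 clause, recurrence. The two instructions are again opposite.
- *A Grade 1 reaction is slowed by 50%, which is Table 6's Grade 1 action, and then becomes Grade 2.* This fits the paragraph's trigger, but it need not meet either Grade 3 clause. There is no necessary conflict.
- *The infusion is resumed with residual Grade 1 symptoms, which simply persist at half rate.* There is no further improvement, but also no recurrence. There is no necessary conflict.

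The overlap is therefore real but partial. It covers the first two cases.

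**Step 2. Look for a text that settles it.** Section 4.1.4.2 requires discontinuation for Grade 3 adverse drug reactions, with listed exceptions, and Section 4.5.1 lists Grade 3 or higher reactions among the reasons for withdrawal. Both need the grade, which is the disputed item. For infusion reactions of Grades 1 to 4, Section 4.1.4.2 refers to Section 5.5.3.1, where both texts stand. Nothing says which prevails.

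**Step 3. What one counted event can do under Section 7.6.** Inputs from Section 7.6: prior beta(0.4, 1.6); looks every 5 patients; Cohort A-C stops if Prob(p > 0.20 | data) exceeds 0.75. Table 8 applies the resulting limits to Cohort D as well. With x events in n patients the posterior is beta(0.4 + x, 1.6 + n − x).

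Table 8 is reproduced first:

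- n = 5: x = 2 gives beta(2.4, 4.6) and 0.778, stop; x = 1 gives beta(1.4, 5.6) and 0.424, continue.
- n = 10: x = 4 gives 0.895, stop; x = 3 gives 0.719, continue.
- n = 15: x = 5 gives 0.856, stop; x = 4 gives 0.687, continue.

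These are the stated limits of 2, 4 and 5. If one related Grade 3 event has already been counted among the first five patients of Cohort A-C or D, counting an infusion reaction in another of those patients moves the look from 1 (0.424, continue) to 2 (0.778, stop).

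**The case against.** The strongest reply is that the two texts can be read in sequence: the paragraph governs while the reaction is Grade 2, and Table 6 takes over once it is Grade 3. The paragraph nowhere says that a Grade 3 reaction may be re-dosed, and an investigator could regrade a reaction that worsens. This has force, but it does not remove the conflict. The paragraph's own trigger includes worsening and gives no instruction to regrade. Nor does the reply help where there is no improvement, because a reaction that fails to improve cannot also be one that responds promptly.

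Two further points narrow the finding. Table 6 gives no time limits for a prolonged or slow response, so a somewhat slow response is not automatically Grade 3. In the text available, the Grade 2 cell also breaks off after mentioning prophylactic medications, so the full cell should be checked; the prompt-response clause itself is intact.

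Three stronger readings are tempting, and the documents do not support them.

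- *Every reaction under the paragraph is contradictory.* The third and fourth cases in Step 1 show otherwise.
- *The safety boundary depends directly on which paragraph is followed.* Adverse events are graded separately by NCI-CTCAE v4.03 (Sections 6.4.1.1 and 7.5.3.3). A reaction recorded as Grade 3 and related counts under Section 7.6, however the subject was managed. The count suffers only if the paragraph's label is carried into the record.
- *A number of affected patients, or a change in early-stopping probability, can be stated.* No share of non-settling reactions is given. Table 5 shows 5 of 32 colorectal patients at 1,200 mg with an infusion reaction, none of Grade 3 or higher. The grade split in Section 2.2.6.1 belongs to the parent antibody. Any rate built from these would rest on assumption.

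**Conclusion.** The conflict stands. For infusion reactions that fail to respond to interruption and treatment, or that return after resumption at half rate, Section 5.5.3.1 both ends M7824 and plans the next infusion, and no other section resolves this. The conclusion comes from reading the two texts together and needs no assumed rate. It does not extend to every case under the paragraph.

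The effect on Section 7.6 is secondary and conditional on the Grade 2 label being used in adverse event recording and on the event being judged related. Its size can be stated only as the one-event shift at a five-patient look shown above, which is equally true of any borderline-graded event. The Table 7 reference is a clerical slip, since the correct table sits immediately above.

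**What to change.** Reconcile Table 6 with the paragraph below it, so that a reaction that does not respond to interruption and treatment, or that returns after resumption, has one grade and one stated consequence for further dosing. Which clinical rule applies is for the sponsor's clinicians to decide. State how the paragraph's remaining cases relate to the table, and change the Table 7 reference to Table 6.

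It would help to add a sentence in Section 7.6 that the count uses the recorded grade, assigned consistently with the reconciled table, whichever management steps were followed.

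The cost is protocol wording only: no extra visits, tests or patients.

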#### 5.5.3.2 Severe Hypersensitivity Reactions and Flu-like Symptoms

If a hypersensitivity reaction occurs, the subject must be treated according to the best available medical practice. A complete guideline for the emergency treatment of anaphylactic reactions according to the Working Group of the Resuscitation Council (United Kingdom) and can be found at https://www.resus.org.uk/pages/reaction.pdf. Subjects should be instructed to report any delayed reactions to the Investigator immediately.

A. Symptoms

- Impaired airway
- Decreased oxygen saturation (< 92%)

- Confusion
- Lethargy
- Hypotension
- Pale / clammy skin
- Cyanosis

#### B. Management

- 1. Epinephrine injection and IV dexamethasone
- 2. Patient should be placed on cardiac, blood pressure, heart rate, and oxygen saturation monitor immediately
- 3. Alert intensive care unit for possible transfer if required

For prophylaxis of flu-like symptoms, a NSAID, for example, ibuprofen 400 mg or comparable NSAID dose, may be administered 2 hours before and 8 hours after the start of each dose of M7824 IV infusion.

#### 5.5.3.3 Immune-Related Adverse Events

For reporting irAE severity/toxicity grading, refer to CTCAE v4.03 toxicity grading system.

For treatment management of irAE per CTCAE v4.03 criteria, refer to American Society of Clinical Oncology (ASCO) Clinical Practice Guidelines and National Comprehensive Cancer Network irAE Management Guidelines.

Treatment of irAEs is mainly dependent upon severity as defined by NCI-CTCAE v4.03. In general, management by CTCAE v4.03 grading, as per ASCO, is listed below:

- Grade 1: study treatment should be continued with close monitoring, with the exception of some neurologic, hematologic, and cardiac toxicities.
- Grade 2: study treatment may be suspended for most Grade 2 toxicities, with consideration of resuming when symptoms revert to Grade 1 or less. Corticosteroids may be administered (initial dose of 0.5 to 1 mg/kg/day of prednisone or equivalent).
- Grade 3: study treatment is generally suspended and the high-dose corticosteroids (prednisone 1 to 2 mg/kg/day) or methylprednisolone 1 to 2 mg/kg/day) treatment should be initiated. Corticosteroids should be tapered over the course of at least 4 to 6 weeks. Some refractory cases may require infliximab or other immunosuppressive therapy.
- Grade 4: in general, permanent discontinuation of study treatment is recommended, with the exception of endocrinopathies that have been controlled by hormone replacement.

Since inhibition of PD-L1 stimulates the immune system, irAEs may occur. Treatment of irAEs is mainly dependent upon severity (NCI-CTCAE grade):

- Grade 1 to 2: treat symptomatically or with moderate dose steroids, more frequent monitoring
- Grade 1 to 2 (persistent): manage similar to high grade AE (Grade 3 to 4)
- Grade 3 to 4: treat with high dose corticosteroids

Treatment of irAEs should follow guidelines set forth in the ASCO/NCCN Management of Immunotherapy-Related Toxicities (https://www.nccn.org/professionals/physician\_gls/pdf/immunotherapy.pdf).

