# 4.1.4.2 Adverse Drug Reactions Requiring Treatment Discontinuation

# The following ADRs, defined as any AE assessed as related to M7824 by the Investigator and / or Merck/EMD Serono, require permanent treatment discontinuation:

Any Grade 4 ADRs require treatment discontinuation except for single laboratory values out of normal range that do not have any clinical correlate, and resolve to Grade  $\leq 1$  or Baseline grade within 14 days with adequate medical management.

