#### Any Grade 3 ADRs require treatment discontinuation except for any of the following:

- Transient (≤ 6 hours) Grade 3 flu-like symptoms or fever, which is controlled with medical management.
- Transient ( $\leq 24$  hours) Grade 3 fatigue, local reactions, headache, nausea, emesis that resolves to  $\leq$  Grade 1 or Baseline grade.
- Tumor flare phenomenon defined as local pain, irritation, or rash localized at sites of known or suspected tumor.
- Any Grade ≥ 3 drug-related amylase or lipase abnormality that is not associated with symptoms or clinical manifestations of pancreatitis. The study principal investigator should be consulted for such Grade ≥ 3 amylase or lipase abnormalities. If the amylase or lipase abnormality not associated with symptoms or clinical manifestations of pancreatitis has not resolved to Grade ≤ 1 within the subsequent 2 doses (28 days), the subject should permanently discontinue treatment with M7824.
- Grade 3 Hgb decrease (< 8.0 g/dL) that is clinically manageable with blood transfusions or erythroid growth factor use does not require treatment discontinuation.
- Increases in Eastern Cooperative Oncology Group performance status (ECOG PS) ≥ 3 that resolves to ≤ 2 by Day 1 of the next cycle (infusions should not be given if the ECOG PS is ≥ 3 on the day of IMP administration and should be delayed until ECOG PS ≤ 2).

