#### Any Grade 2 ADR should be managed as follows:

- If a Grade 2 ADR resolves to Grade  $\leq$  1 by the last day of the current cycle, treatment may continue.
- If a Grade 2 ADR does not resolve to Grade ≤ 1 by the last day of the current cycle but it is manageable and / or not clinically relevant, the ADR should be discussed with the principal investigator and based upon discussion it is possible the infusion will be given on the following cycle. If at the end of the following cycle, the event has not resolved to Grade 1, discussion should be had with the principal investigator about permanently discontinuing treatment with M7824.

- Upon the second occurrence of the same Grade 2 ADR in the same subject (except for fatigue and hormone insufficiencies that can be managed by replacement therapy), continuation of treatment with M7824 has to be discussed with the principal investigator and might be permanently discontinued.
- Infusion-related reactions and hypersensitivity reactions (Grades 1 to 4) should be handled according to the guidelines provided in Sections **5.5.3.1 and 5.5.3.2**, respectively.
- Anemia should be handled according to the guidelines provided in Section **5.5.3.4**.

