### 4.5 Criteria for Subject Withdrawal

#### 4.5.1 Withdrawal from Trial Treatment

Subjects will be withdrawn from trial treatment for any of the following reasons:

- PD as defined by iRECIST 1.1
  - Patients may continue on M7824 until immune confirmed PD (iCPD) provided they meet the criteria for pseudoprogression (see 5.5.1.1 below)
- Therapeutic failure requiring urgent additional cancer therapy
- Occurrence of any Grade ≥ 3 ADRs or repetitive Grade 2 ADRs as defined in Section 5.5.3.3.
- Occurrence of AEs, at the Investigator's discretion
- Pregnancy
- Use of prohibited concomitant drug, as defined in Section 5.5.2, where the predefined consequence is withdrawal from the IMP
- Non-adherence / non-compliance to the trial protocol or trial requirements (see Section 5.9)
- Withdrawal of consent
- Participation in any other trial

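### Section 4.1.4.2 permanently stops M7824 for related Grade 3 events, section 5.5.3.3 suspends it for immune-related ones; they also differ on hormone-controlled Grade 4 endocrinopathies, and neither is said to prevail

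*Combined protocol and SAP*

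**What the plan says.** Section 4.1.4.2 covers adverse drug reactions, "defined as any AE assessed as related to M7824 by the Investigator" (or by the drug's manufacturer), and says that those it lists "require permanent treatment discontinuation".

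- **Grade 3:** "Any Grade 3 ADRs require treatment discontinuation", followed by a list of exceptions: short-lived flu-like symptoms or fever; short-lived fatigue, local reactions, headache, nausea or emesis; tumor flare; amylase or lipase abnormality without pancreatitis; manageable hemoglobin decrease; and a temporary worsening of performance status.
- **Grade 4:** "Any Grade 4 ADRs require treatment discontinuation except for single laboratory values out of normal range", provided these have no clinical correlate and resolve within 14 days.
- **Grade 2:** a second occurrence of the same reaction prompts a discussion about stopping, "except for fatigue and hormone insufficiencies that can be managed by replacement therapy".

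The same section sends some reactions elsewhere. Infusion and hypersensitivity reactions go to 5.5.3.1 and 5.5.3.2. For anemia it says "Anemia should be handled according to the guidelines provided in Section" 5.5.3.4. It sends no irAE to 5.5.3.3.

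Section 5.5.3.3, on irAEs, says "Grade 3: study treatment is generally suspended" and adds high-dose corticosteroids. At Grade 4 it recommends permanent discontinuation in general, but exempts endocrinopathies controlled by hormone replacement.

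Section 4.5.1 lists as a reason for withdrawal from treatment: "Occurrence of any Grade ≥ 3 ADRs or repetitive Grade 2 ADRs as defined in Section 5.5.3.3".

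**The concern.** Section 2.1.1 describes irAEs as identified risks and adverse reactions of M7824, so a related irAE falls under the general rule of 4.1.4.2 as well as the specific text of 5.5.3.3. For some of these events the two texts prescribe different consequences. An investigator who follows one departs from the other.

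The choice matters for the patient and for the data:

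- whether a patient with a severe reaction may be re-dosed, and hence exposure and time on treatment;
- the last-dose date, which anchors the 30-day treatment-emergent window (7.5.3.1 and 7.5.3.3) and the 90-day safety window (6.4.1.1.1 and 7.6);
- eligibility for retreatment, which 6.1.2 denies to anyone whose toxicity led to discontinuation of the initial course;
- the summary of premature terminations by primary reason (7.5.3.3).

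**Working it through.** The plan states no figure for this point. The check is a reading of the texts side by side, followed by an illustration of frequency.

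**Step 1. The same event under each section**

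| Event, assessed as related | 4.1.4.2 | 5.5.3.3 |
|---|---|---|
| Grade 3 irAE outside the exception list, e.g. adrenal insufficiency | Permanent discontinuation | Generally suspended; silent on resumption |
| Grade 4 endocrinopathy controlled by hormone replacement, more than an isolated laboratory value | Permanent discontinuation | Exempt from permanent discontinuation |
| Other Grade 4 clinical irAE | Permanent discontinuation | Permanent discontinuation recommended in general |

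The first two rows conflict and the third does not.

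**Step 2. Does another section settle it?**

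- 4.1.4.1 refers to 5.5.3 for details of discontinuing, withholding and restarting, without ranking the two texts.
- 2.1.1 and 2.2.6.2 refer to 5.5.3.3 for irAE management and for instructions on discontinuing or interrupting treatment. Neither says that 5.5.3.3 overrides 4.1.4.2.
- 4.5.1 uses 5.5.3.3 as the source of a definition of the Grade 3 or higher and repeated Grade 2 reactions that lead to withdrawal. Section 5.5.3.3 holds no such definition, and its Grade 3 text speaks of suspension.
- The hormone exception in 4.1.4.2 applies only to a repeated Grade 2 reaction.
- 5.5.3.7 allows interruption and resumption, but only for events not related to study drug.

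None of these resolves the conflict.

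**Step 3. How often could it arise?**

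Inputs: section 2.1.1 reports 32 colorectal patients at 1,200 mg, with one related Grade 3 adrenal insufficiency and one related Grade 3 enteritis. Section 2.1.1 lists adrenal insufficiency among the irAE risks. The documents do not say that the enteritis was immune-related. Planned numbers (4.1.2) are 15 in Cohort A-C, 15 or 29 in Cohort B, and 15 in Cohort D.

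- Full enrollment: 15 + 29 + 15 = 59. If Cohort B stops at stage 1: 15 + 15 + 15 = 45.
- Expected cases = n × p. P(at least one) = 1 − (1 − p)^n. Confidence intervals are exact binomial.

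| Assumption | p (exact 95% CI) | n | Expected (p at the CI limits) | P(at least one) |
|---|---|---|---|---|
| Adrenal insufficiency only | 1/32 = 3.1% (0.1% to 16.2%) | 59 | 1.8 (0.05 to 9.6) | 0.846 |
| | | 45 | 1.4 (0.04 to 7.3) | 0.760 |
| Enteritis also immune-related | 2/32 = 6.3% (0.8% to 20.8%) | 59 | 3.7 (0.5 to 12.3) | 0.978 |
| | | 45 | 2.8 (0.3 to 9.4) | 0.945 |

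These counts concern the Grade 3 conflict. Section 2.1.1 reports no related Grade 4 event in those 32 patients, so it gives no observed case of the Grade 4 conflict.

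**The case against.** The best counter-argument is that the specific rule governs. Sections 2.1.1, 2.2.6.2, 4.1.4.1 and 4.5.1 all point to 5.5.3 or 5.5.3.3, so 5.5.3.3 could be read as the operative text for irAEs. That reading is arguable, but it is not written down. 4.1.4.2 is mandatory, and it defers infusion reactions, hypersensitivity and anemia by name while leaving irAEs out. The hedged wording of 5.5.3.3 does not reconcile it with a mandatory stop.

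Other limits stand, and they rule out stronger readings that a reader might infer:

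- **That the two sections direct opposite handling throughout.** At Grade 3 dosing stops under both. The difference is permanence, and 5.5.3.3 does not expressly authorize a restart. Its Grade 2 text mentions resuming and its Grade 3 text does not. The contrast with permanent discontinuation at Grade 4 suggests that suspension is not meant to be permanent, but this is inference. At Grade 4 the difference is confined to hormone-controlled endocrinopathies.
- **That about 7 patients would be affected (4/32 × 59 = 7.4).** The 4 subjects include the anemia and raised-bilirubin events, which the documents do not call immune-related. Manageable Grade 3 hemoglobin decrease is itself an exception in 4.1.4.2.
- **That the primary analysis is compromised.** ORR is calculated over all treated patients (7.5.2.1.1), and in Cohorts A-C and B those who stop for toxicity stay on imaging until progression (4.1.1.1, 4.1.1.2). Related Grade 3 or higher events count toward the 7.6 toxicity boundaries under either text, subject to that section's own qualification for laboratory values.

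The retreatment consequence reaches only responders who progress after stopping. The trial runs in one department of one institution (section 1), which limits divergent handling between sites but does not tell that department which text to follow.

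**Conclusion.** Wrong as written: an internal contradiction on a safety rule. It covers related Grade 3 irAEs outside the 4.1.4.2 exception list and Grade 4 endocrinopathies controlled by hormone replacement, together with a 4.5.1 cross-reference that leads to no definition. This conclusion rests on the text alone and depends on no event rate.

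The illustration suggests that at least one Grade 3 case is likely. It assumes that a rate based on one event, or two, in 32 patients carries over to different populations: Cohort A-C excludes patients with earlier serious irAEs, Cohort B adds radiotherapy, and Cohort D is resected. The 59-patient figures also assume that Cohort B reaches stage 2, whereas 7.1.2 gives an 82.9% chance of early termination under the null. The consequences fall on patient management and safety reporting; the ORR denominator is unchanged.

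**What to change.** Reconcile 4.1.4.2, 4.5.1 and 5.5.3.3 into one rule for Grade 3 irAEs and for hormone-controlled Grade 4 endocrinopathies. State which section prevails for irAEs. Say explicitly whether dosing may resume after a Grade 3 suspension. Make 4.5.1 refer to a place where the withdrawal criteria are actually defined. The sponsor's clinicians must decide which rule applies; this review takes no view on that.

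The cost is protocol amendment wording. The sample size and the primary analysis are not affected.
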